8.4 Routine Adverse Event Reporting Guidelines

The descriptions and grading scales found in the revised NCI CTCAE version 4.0 will be used for adverse event reporting to the institutional IRB, DSMC, and sponsor. The IRB Reportable Events Forms

(http://researchintegrity.weill.cornell.edu/forms_and_policies/forms/Immediate_Reporting_Policy.pdf) should be used for all reportable adverse events.

8.5 Safety Profile of LY2157299

Mild to Moderate (Related to LY2157299):

Diarrhea (12%), Fatigue (26%), Anemia (14%), Nausea (15%), Vomiting (10%), Abdominal pain (14%), Headache (13%), Neutropenia (5%), Anorexia (4%), Pruritus (4%), Constipation (3%).

IND # 126952

Protocol # 1505016222
Version Date 04/21/2017

Possible Side Effects related to LY2157299:

Neutropenia, Thrombocytopenia, Lymphopenia, Leukopenia, Dysgeusia, Anorexia, Abdominal Discomfort, Dyspepsia, Pruritus, Dehydration, Asthenia, elevated liver enzymes, elevated creatinine.

Rare but Serious side effects related to LY2157299:

Pneumonia/Lobar Pneumonia, Pulmonary embolism, Deep vein Thrombosis, Sepsis, Neutropenia, Ascites, Anemia, Neoplasms, Pancreatitis, Asthenia, Retroperitoneal Hematoma, Heart attack, Stroke, Atrial Thrombosis, Heart Failure.

Death resulting from side effects considered related to LY2157299 in less than 1% of subjects have been reported.

9 CORRELATIVES AND SPECIAL STUDIES

9.1 Laboratory Correlatives Studies

Immune-monitoring studies will be conducted at UCLA under the supervision of [name] as well as at WCM under the direction of [name] and [name]. Blood samples will be obtained at baseline, and weeks 2, 5 and 15 for immune monitoring. All samples obtained for immune-monitoring studies will be processed for assay testing at the respective sites of collection. The following analyses will be performed:

9.1.1 TGF β gene response signature

Assessment of TGF β gene response signature (TBRS) positivity in primary tumors or metastases as predictive biomarker of response to palliative LY2157299 plus radiation therapy combination therapy will be conducted.

We will use the 153-gene TGF β response signature (TBRS) developed by Massague` and colleagues. TBRS identified TGF β activity in 38/67 of metastatic lesions extracted from bones, lungs and other sites representing the natural metastatic spectrum of human breast cancer samples [72]. The resulting data will be processed by the WCM Core to ascertain the degree of TBRS in each patient; the study Biostatistician and staff will evaluate the associations with

outcomes. We predict that the presence of TBRS in the primary or metastatic cancer will predict tumor response to RT+LY2157299. Based on past experience, we assume that approximately 50% of subjects will have TBRS-positive tumors. Subjects who have TBRS-positive tumor and derive clinical benefit will be considered true positive.

9.1.2 Circulating Levels of TGF β

Monitoring of circulating levels of TGF β prior to, during and after radiation therapy in patients with metastatic breast cancer before and after LY2157299 treatment. We recognize that TGF β measurements are complicated by the presence of the neutralizing antibody. We will develop a new ELISA design based on LAP antibodies to overcome this limitation, in collaboration with [name] at NYU. Plasma TGF β levels will also be measured.

9.1.3 Anti-angiogenic Activity of LY2157299 in vivo

Exploration of whether LY2157299 has anti-angiogenic activity *in vivo* by comparing circulating VEGF levels in plasma before and after treatment (ELISA). Plasma VEGF levels will be measured.

9.1.4 Tumor specific Immune responses

The most accepted technology for assessing T-cell responses to tumor antigen, namely ELISPOT and tetramer assays will be used. ELISPOT assays measure local release of cytokines by activated T cells following *ex vivo* re-stimulation by antigen. IFN γ production is most often used as a surrogate marker of T cell-mediated anti-tumor immunity. ELISPOT can be as sensitive as the tetramer assay and can be adapted to measure T cell avidity, although this will not be performed in this study, as it is not relevant to its aims. However, ELISPOT will be used to measure the hierarchy of epitope-specific responses for survival, since this might increase following radiation-induced tumor cell death, and indicate epitope spreading which we believe is an important correlate of clinical response [73].

The MHC tetramer assay uses flow cytometry to enumerate individual CD8 T lymphocytes that specifically recognize a peptide antigen of choice. Tetramers specific for CD4 or CD8 T cells are available, though MHC-I tetramers only will be used as they are more advanced. The tetramer assay is very able to detect expected increased responses in PBMCs from patients receiving RT. A detailed statistical analysis on data obtained with repeated sampling of over 100 patient

samples at UCLA showed that if antigen-specific T cells started below the lower limit of detection of 0.038%, they could be considered to have been boosted if they had an increase to over 0.066%, representing the mean + 3 standard deviations (unpublished). The assay does not require *ex vivo* T cell clone expansion, minimizing possible artifacts. It is chosen primarily because it directly quantifies tumor-specific CD8 T cells. However, it does not assess the functional status of cells; which is why both tetramer staining and ELISPOT assays will be performed, but with the expectation of a direct correlation. A lack of correlation would indicate involvement of divergent mechanisms that would be investigated further, depending on the results.

All 4 longitudinal samples from 5 HLA-A2 patients will be tested at one time using one vial of cells, in parallel with PBMCs from controls. Initially, PBMCs from HLA-A2+ patients, who should be 45% of the cohort, will be tested for CD8+ T cells that bind tetramers containing the (LMLGEFLKL) survivin peptide, which has a high binding affinity for HLA-A2 [69] and, for patients whose tumors are also HER2/neu positive, also the HER:p369-377 peptide [74]. The usual controls will be included, including a nonsense tetramer and PBMCs from controls, as described previously [71]. If ELISPOT assays indicate utility, non-HLA-A2 patients will be tested by tetramer assay using peptides immunodominant for their known HLA type [68-69].

9.1.5 Levels of circulating Tregs

Tregs will be detected primarily by staining PBMCs with antibodies for CD25, CD4, and intracellular FoxP3 (FACS analysis). Additional markers will be CD127, CD45RA/RO, and CTLA4. We include an examination of CTLA-4 because CTLA-4 signaling seems to be required for Treg function, possibly through TGF- β induction [75-76]. In addition, the NYU team has shown in preclinical models that anti-CTLA-4 synergizes with RT. CD45RA/RO and CD127 will be included because of recent reports that these mark subsets of Tregs with distinct proliferative and migratory properties that are relevant to cancer [77]. CD25, CD4, and intracellular FoxP3 staining will be performed at the same time as tetramer staining (see above) but another vial of each sample will be used for additional evaluation of Treg function, performed as previously described [71].

9.2 Collection of Specimen(s)

Peripheral blood for immune monitoring will be obtained from all trial participants at 5 time points: 1) baseline, 2) day 14; 3) day 42 infusion and 4) time of disease evaluation, at week 15. Blood will be drawn prior to radiation since radiation may increase TGF β levels as shown in animal models. Up to an average of 60 ml of peripheral blood for research purposes will be collected at each time point into EDTA Lavender top tubes from consented patients enrolled in the trial, for analysis of plasma and PBMCs.

Tissue biopsy is not mandatory for participation in the trial, but archived tumor samples (slides and blocks, where available) will be obtained from consented patients. This tissue may be utilized to study TGF β response expression signatures.

Sample collection is described in more detail in Appendix 1.

9.3 Handling of Specimens

PBMCs will be isolated within 24 hours of blood draw. Plasma will be stored for measurements of circulating TGF β . An aliquot of 2×10^6 cells will be removed for HLA typing. DNA isolated with the QIAamp DNA Blood Mini prep kit (Qiagen) will be submitted to the UCLA Immunogenetics Center (UIC) for PCR-based HLA typing that allows accurate and reliable results in resolving allele-level differences. The UIC is internationally recognized as a pioneer in HLA typing and crossmatch testing for tissue and organ transplants and a World Health Organization reference laboratory for HLA typing. Remaining cells will be frozen in 4 x 1 ml aliquots in 10% DMSO in human AB serum and plasma in 2.5 ml cryovials. Samples will be stored initially at -80C and then liquid N2 until used. All freezers will have alarm systems to avoid sample loss. Batches of PBMCs will be sent on dry ice overnight to UCLA from the other centers and plasma samples similarly shipped to WCM, one vial set at a time to prevent complete loss of samples due to unlikely shipping delays. All samples will be coded for laboratory analysis. A master list with the patient's name and an identification number will be kept in a locked cabinet.

9.4 Storage of Samples

Serial blood samples for immune monitoring collected at baseline, and at selected time points outlined in section 5.10.

IND # 126952

Protocol # 1505016222
Version Date 04/21/2017

All blood and tissue samples will be stored in a -80°C locked freezer in the WCM Bio repository for an indefinitely for research purposes only. These specimens will not be linked to any clinical data and will be de-identified in the clinical research database - only the data manager will have access to the master list with the patient name and an identification number. This master list will be secured in a locked cabinet at the WCM. Only the investigators listed on this protocol will have access to these samples as is described in sections 9.1.1-9.1.5.

The storage of your blood and tissue is optional and you may withdraw your consent for the banking of these specimens at any time. You may make this request by writing to the Principal Investigator [name]. at Weill Cornell Medicine, [name].

9.5 Shipping of specimens

Frozen blood specimens from WCM will be de-identified and shipped to UCLA at -80°C.

9.6 Site(s) Performing Correlative Study

Correlative studies (as described in sections 9.1.1-9.1.5) will be performed at UCLA.

9.7 Coding of Specimens for privacy protection

All patients enrolled will be given a unique identifier (study ID number). Only the data manager will know the code linking patient and study ID number. Patients will be assigned a unique code number. All specimens collected will be de-identified and assigned the same unique study number of the corresponding patient and will also be marked with the collection time point. Clinical information regarding toxicities and response will likewise be stored in a de-identified database using only the unique identifier (study ID number).

10.3 Conflict of Interest

There are no conflicts of interest to declare.

11 MEASUREMENT OF EFFECT

Abscopal responses will be assessed at 15 weeks based on [78] (Table 2). This choice of this interval is to enable a sufficient length of study to detect abscopal responses. In fact, the experience in the clinical trials of Ipilimumab in melanoma demonstrated occasional initial progression of disease with appearance of new metastatic sites when compared to the baseline imaging assessment. “Flares” at the first PET/CT or CT(Chest/Abdomen/Pelvis) assessment were often followed by clinical responses to the antibody. While the mechanism of action of

Ipilimumab is different from that of LY2157299, the experience with TGF β inhibition in malignant glioma reported by Hau et al [79] confirms the lesson from the melanoma trials, i.e. that whenever the response is mediated by the immune system the following course is likely to manifest: 1) achievement of a clinical and radiological measurable response is slower than that of a typical response to cytotoxic therapy (RT or chemotherapy); 2) it can be heralded by an initial “flare” or emergence of new metastatic sites and, 3) with time it may be dramatic and would have been missed if the drug was discontinued too soon [80] [81].

Table 2: Immune response criteria (irRC)

	Summary of irRC
Note:	New, measurable lesions are incorporated into tumor burden
CR	Disappearance of all index and non-index lesions in two consecutive observations not less than 4 weeks apart, without the development of any new lesions.
PR	$\geq 50\%$ decrease in tumor burden compared with baseline in two observations at least 4 weeks apart
SD	50% decrease in tumor burden compared with baseline cannot be established nor 25% increase compared with nadir
PD	At least 25% increase in tumor burden compared with nadir (at any single time point) in two consecutive observations at least 4 weeks apart

11.1 Anti-tumor Effect

11.1.1 Definitions

Patients will be evaluated by PET/CT or CT(chest/abdomen/pelvis) at baseline, week 5 and week 15. However, systemic anti-tumor response will be by PET/CT or CT(chest/abdomen/pelvis) as defined by irRC at 15 weeks (primary endpoint).

Patients who have received at least one 14 days cycle of the study drug will be followed for toxicity (lack of grade 4 toxicity— primary safety end point). Patients will receive a total of 14 doses of LY2157299 (one dose daily for 14 consecutive days), per cycle. Patients who have received any treatment will also be evaluated for abscopal response to the metastatic sites using the immunologic response criteria based on the 5 and 15 week PET/CT or CT(chest/abdomen/pelvis) scans as outlined above in Table 2.

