5. TREATMENT PLAN

5.1 Investigational Agent or Device Administration

Enrolled patients will receive 300 mg/day of LY2157299. LY2157299 will be administered as an oral drug tablet.

The study drug will be administered orally on a 28-day cycle (1 cycle=28 days), every 2 weeks, or 14 days on / 14 days off. Blood samples will be obtained at baseline, and weeks 2, 6 and 15 for immune monitoring. Imaging by PET/CT or CT(Chest/Abdomen/Pelvis) will be performed at baseline, 5 weeks and 15 weeks. The chosen metastatic sites will receive conformal external beam radiation 7.5 Gy/fraction x 3, to a total of 22.5 Gy over the course of one week (on alternating days):

- lesion 1 will be irradiated at week 1 (RT starts 1 day after 1st dose of LY2157299),
- lesion 2 will be irradiated at week 5 (RT starts after 1stdose of the second cycle of LY2157299)

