5.3 On-Study Evaluations

(See study calendar, section 5.10)

1. Physical exam: including complete skin evaluation and evaluation of oral mucosa prior to start of **each** RT cycle and **prior** to each LY2157299 administration.
2. Hematology: CBC with differential and platelet count and peripheral blood smear. PT/INR,PTT should be evaluated following multiple doses of LY2157299; Serum chemistries: Electrolytes (sodium, potassium, chloride, and bicarbonate), BUN, creatinine, glucose, and liver function tests (AST, ALT, ALP, total bilirubin, LDH, and Troponin I C). These will be carried out prior to start of each RT cycle and prior to each cycle of 2 weeks of BID LY2157299 administration.
3. ECHO/Doppler : Week 8 within 5 days prior to starting week 9 LY2157299 administration and Week 15
4. Study Special Tests: TGF β levels (at wk 1 day -1 and week 15 visit), immune evaluation at weeks 1 day -1, 2, 5 and 15 LY2157299 PK (pre- & after completion of drug cycle day 14 & at day 42).
5. Tumor measurement by PET/CT/ CT(chest/abdomen/pelvis) at weeks 5 and 15.
6. Adverse events evaluated and recorded using the NCI CTCAE version 4.0 throughout the treatment period (weeks 0-15).

To date, LY2157299 at the planned dose for this study is well tolerated in patients. If a toxicity is observed, a dose reduction may be considered based on the aggregate safety information of LY2157299, if other plausible reasons for a toxicity have been excluded.

Specifically, no bone marrow toxicities were detected in nonclinical toxicology studies; 1 toxicity was reported in a patient with glioblastoma in whom a Grade 4 thrombocytopenia was observed and this toxicity was potentially associated with administration of LY2157299 monotherapy. If a similar case occurs, the drug should be discontinued until platelet counts either return to Grade 1 or baseline.

If a patient experiences any of the following events that are considered possibly related to LY2157299 and not to study disease, LY2157299 will be omitted until the event resolves:

- Grade 4 Thrombocytopenia
- Grade 3 thrombocytopenia associated with bleeding
- Grade 4 Anemia
- absolute neutrophil count (ANC) $<0.5 \times 10^9/L$ for longer than 7 days, or ANC $<1.0 \times 10^9/L$ with a single temperature of $>101^{\circ}\text{F}/38.3^{\circ}\text{C}$ or a sustained temperature of $>100.4^{\circ}\text{F}/38^{\circ}\text{C}$ for more than 1 hour, or platelet count $<25,000 \times 10^9/L$

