- Common Terminology Criteria for Adverse Events Grade 3 or 4 non-hematologic toxicity

Non-hematologic and hematologic toxicity must resolve to CTCAE Grade 0, 1, or baseline (with the exception of alopecia, fatigue, skin rash, nausea, vomiting, constipation, or diarrhea that can be controlled with treatment) before start of next cycle. If recovery is >29 days (Day 1 of the next cycle), patient must be withdrawn from study treatment.

If moderate or severe heart valve toxicities are observed, or the patient develops aneurysms of the great vessels of the heart, the patient must immediately be discontinued from the treatment and the toxicity reported to sponsor within 24 hours (see references on the ECHO assessment based on the Guidelines of the American and European Societies of Cardiac Echocardiography). If the patient develops new cardiovascular lesions in the chest, an MRI or CT with contrast of the abdomen should be performed to evaluate for development of abdominal vascular lesions. Exceptions to this rule must be approved by the IRBs and sponsor.

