12.1 Monitoring plan

This study will be conducted in accordance with the guidelines in the 2001 NCI approved data Safety and Monitoring plan for the WCM Cancer Institute and with the UCLA approved data Safety and Monitoring plan for the UCLA Cancer Institute. Reports to the Data Safety and Monitoring Committee will include the following information: accruals, targets, responses, adverse events and evidence of reporting to appropriate review committees. The WCM Data and Safety Monitoring Board (DSMB) will review the IRB approved protocol, the data and safety monitoring plan and any stopping guidelines during protocol initiation. The WCM DSMB is to perform a data and safety analysis annually (as per DSMB letter dated 04.20.2017) following the accrual of the first subject. . The WCM DSMB may also convene as needed if stopping criteria are met or other safety issues arise that the Principal Investigator and/or IRB would like the WCM DSMB to address.

As per WCM DSMB recommendations, the safety analysis will be performed annually, at which point the protocol and safety analysis should be submitted to the DSMB for review.

12.2 Stopping rules (for the individual patient and for the study as a whole)

Patients will be discontinued from study therapy when any clinical adverse event greater than Grade 3 or intercurrent illness in the opinion of the Principal Investigator, indicates that continued treatment with the study therapy is not in the best interest of the subject. Patients will be monitored until the resolution of the adverse event. Based on PI's discretion, patients will resume or will be withdrawn from the study therapy.

If five or more non-hematological toxicities, Grade 3 and above, are reported over a period of 3 months, will result in temporary discontinuation of combination therapy.

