14.1.2 Secondary endpoints

1. To estimate the local response rate of combining TGF β receptor I kinase inhibitor LY2157299 and local radiotherapy
2. To determine if treatment with TGF β receptor I kinase inhibitor LY2157299 and

localized RT enhances tumor-specific immunity in patients with metastatic breast cancer, and if this is associated with abscopal tumor regression.

3. To determine if treatment with TGF β receptor I kinase inhibitor LY2157299 and localized RT alters the numbers and function of T-reg cells in patients with metastatic breast cancer.

A. Analysis Populations

Efficacy analysis will be conducted on all patients who are entered into the study and received any treatment. Additional supportive efficacy analyses will be conducted for those patients who have completed week 15 visit.

B. Sample Size

i. Accrual estimates

Expected number of eligible patients will be 4 per month.

ii. Sample size justification

In this trial, a total of 28 patients with metastatic breast cancer will be accrued both at WCM and at UCLA (18 patients at WCM and 10 patients at UCLA) to treatment with radiotherapy + 300 mg/daily LY2157299 for 14 days on / 14 days off, and followed for evaluation of abscopal responses based on the immune response criteria at 15 weeks. With 28 patients enrolled in this study, we can test the null hypothesis that the abscopal response rate at 15 weeks is ≤ 0.05 versus the alternative that the response rate is 0.19 with $\alpha = 0.05$ and power of 80%. If there are 3 or fewer responses in the 28 patients, then the combination will be rejected for further study in this single stage design (calculations from PASS 2008, J. Hintze, NCSS, Kaysville, Ut). The trial is designed to allow for up to 56 patients to be enrolled to ensure that 28 patients will be evaluable at 15 weeks. Response rates will also be estimated for all enrolled patients.

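### As written, the primary safety endpoint leaves out patients who stop for good before completing a 14-day drug course, and its grade 4 wording does not expressly include grade 5

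*Combined protocol and SAP*

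**What the plan says.** Section 1.1 makes safety and feasibility of the combination a primary objective. Section 14.1.1 repeats that objective without defining a measure. The measure appears only in section 11.1.1: "Patients who have received at least one 14 days cycle of the study drug will be followed for toxicity", followed in brackets by "lack of grade 4 toxicity" as the primary safety endpoint. The next sentence describes a cycle as 14 daily doses on consecutive days.

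The same paragraph then assesses abscopal response in patients who received any treatment. Section 14.1.2, part A, does likewise: "Efficacy analysis will be conducted on all patients who are entered into the study and received any treatment". Part A names no safety population, and section 13 describes no safety analysis.

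On exposure, section 5.1 says of the first lesion that "RT starts 1 day after 1st dose of LY2157299".

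On interruption and stopping, section 5.3 says that for listed events "LY2157299 will be omitted until the event resolves". It adds "If recovery is >29 days (Day 1 of the next cycle), patient must be withdrawn from study treatment", and for moderate or severe valve toxicity or aneurysm of the great vessels, "the patient must immediately be discontinued from the treatment". Section 5.7 allows removal from treatment for an intolerable adverse event. Section 12.2 leaves resumption or withdrawal after an event above grade 3 to the investigator.

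On grade, the study-level stopping rule in section 12.2 counts "five or more non-hematological toxicities, Grade 3 and above", which is open-ended upwards.

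**The concern.** A safety set that requires completion of a course is conditioned on something toxicity can prevent. The documents list several toxicity-related routes to permanent stopping. If one of them operates during the first course, the patient never qualifies for the endpoint that is meant to capture the event. A patient whose drug is held and who later completes a course still counts, so the problem is confined to permanent early stoppers.

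The grade wording raises a second, smaller point. Taken literally, an endpoint of no grade 4 toxicity does not say what happens to a grade 5 event. Section 8.5 reports deaths considered related to LY2157299 in under 1% of subjects, so a fatal event cannot be ruled out.

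What is at stake is the headline safety result for a new combination in a small single-arm study, where one or two patients move the estimate by several percentage points.

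**Working it through.** **1. The plan's own figures.** The only sized hypothesis concerns abscopal response (section 14.1.2, part B): N = 28, null rate 0.05, alternative 0.19, rejection of the combination at 3 or fewer responses. Exact binomial: P(X ≥ 4 | 28, 0.05) = 0.0491 and P(X ≥ 4 | 28, 0.19) = 0.8065. These agree with the stated alpha of 0.05 and power of 80%. No target rate, precision or threshold is given for safety, so there is no safety figure to reproduce.

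**2. The populations side by side.**

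| Purpose | Who counts | Section |
|---|---|---|
| Primary safety endpoint | Received at least one 14-day cycle | 11.1.1 |
| Abscopal response | Received any treatment | 11.1.1 |
| Efficacy analysis | Entered and received any treatment | 14.1.2, part A |
| Adverse event follow-up | After any administration of drug | 8.2 |
| Adverse event recording | Weeks 0–15 | 5.3 |

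The narrowest condition is attached to the safety endpoint. Sections 8.2 and 5.3 secure the data for early stoppers but do not put those patients into the endpoint.

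**3. Effect on the rate.** Let n patients be treated, of whom x have a grade 4–5 event, and let k of those x stop for good before completing a course. Counting all treated patients gives x/n. The literal set gives (x − k)/(n − k). Because x < n, the literal rate is lower whenever k > 0. Other early stoppers without an event are taken as none.

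The documents give no overall grade 4–5 rate and no early-stop rate, so x and k are assumed. With n = 28, x = 4 and exact (Clopper-Pearson) 95% limits:

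| k | Literal set | Rate | 95% CI |
|---|---|---|---|
| 0 | 4/28 | 14.3% | 4.0–32.7 |
| 1 | 3/27 | 11.1% | 2.4–29.2 |
| 2 | 2/26 | 7.7% | 0.9–25.1 |
| 4 | 0/24 | 0% | 0–14.2 |

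With a single event (x = 1), all treated gives 1/28 = 3.6% (0.1–18.3). If that patient stops early, the literal set gives 0/27 = 0% (0–12.8).

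**4. Grade 5 alone.** Suppose all 28 complete a course, one patient has a grade 5 event and there is no grade 4 event. Not counting grade 5 gives 0/28 = 0% (0–12.3). Counting it gives 1/28 = 3.6% (0.1–18.3).

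**5. Other enrolment figures.** The Protocol Summary gives an accrual ceiling of 35, and section 14.1.2, part B, allows up to 56. One omitted event, as a share of all treated, would then be 1/35 = 2.9% or 1/56 = 1.8%.

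**The case against.** The best counter-argument is that section 11.1.1 describes follow-up and does not state a denominator. It sits under a heading on anti-tumor effect, gives no proportion, and uses the same verb that section 8.2 applies to all adverse events after any dose. To receive a cycle could also mean to start one, and section 5.1 defines a cycle as 28 days, so the qualifying exposure is loosely drafted. This shows ambiguity, but it supplies no other safety set. The 14-dose sentence and the contrast with any treatment in the same paragraph both favor the completed-course reading, and a primary endpoint should not depend on which reading the analyst picks.

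Several points about likelihood and size do stand:

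- The first scheduled on-study echocardiogram is at week 8, so valve toxicity or aneurysm would be found during a first course only if it presented clinically.
- Section 8.5 puts related deaths below 1%. That implies fewer than 28 × 0.01 = 0.28 such deaths among 28 patients, although the figure covers neither grade 4 events nor the combination with radiation.
- The row with k = 4 is an extreme case, and the intervals overlap heavily (4.0–32.7 against 2.4–29.2 for k = 1).
- No go/no-go rule uses this rate. Serious adverse event reporting, the stopping rule and board review carry no such restriction.
- Grade 5 was probably meant to count, so that part is a clarification.

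**Conclusion.** The point holds. The only definition of the primary safety endpoint is tied to a completed 14-day course, nothing in sections 13 or 14 overrides it, and the documents' own stopping provisions mean that the loss of patients can depend on the outcome being measured. Any resulting bias is downwards. Its size rests on assumed counts: none if no patient with an event stops early; 14.3% falling to 11.1% or 7.7% if one or two of four do; and a single event in 28 (3.6%) becoming 0% if that patient does. The defect is in the endpoint definition and does not weaken safety monitoring. It should be fixed. The grade 5 wording is a minor accompanying clarification.

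**What to change.** Amend section 11.1.1, and add the same text to the analysis populations in section 14.1.2:

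- The safety set is every patient who received any dose of LY2157299 or any study radiation.
- The primary safety endpoint is the proportion of that set with a grade 4 or 5 toxicity, reported with an exact 95% confidence interval.
- Report the number of patients who stopped before completing a first 14-day course, with reasons.

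The two cycle lengths (14 days in section 11.1.1, 28 days in section 5.1) should also be reconciled in the text. The endpoint above does not depend on how that is settled.

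The cost is about two sentences in each place. The data are already collected under sections 5.3 and 8.2. N, alpha, power, dosing and stopping rules stay as they are. The one drawback is that the reported toxicity rate may be less favorable.

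### The primary safety end point is tied to patients who completed a 14-day cycle, so patients permanently stopped for early Grade 4 toxicity can fall outside it

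*Combined protocol and SAP*

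**What the plan says.** All references are to the combined protocol and SAP.

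- **Safety end point (11.1.1).** "Patients who have received at least one 14 days cycle of the study drug will be followed for toxicity", with the end point given in parentheses as "lack of grade 4 toxicity" and labelled the primary safety end point. The next sentence describes a cycle: "Patients will receive a total of 14 doses of LY2157299 (one dose daily for 14 consecutive days), per cycle".
- **Response (11.1.1, same paragraph).** The group is wider: "Patients who have received any treatment will also be evaluated for abscopal response".
- **Analysis populations (14.1.2 A).** "Efficacy analysis will be conducted on all patients who are entered into the study and received any treatment". A supportive efficacy set of week 15 completers follows. No safety set is listed there or elsewhere. Section 14.1.1 repeats the safety objective without a denominator.
- **Stopping for toxicity (5.3).** After a listed event thought possibly related to the drug, "LY2157299 will be omitted until the event resolves". If recovery takes more than 29 days, the "patient must be withdrawn from study treatment". Moderate or severe valve toxicity, or an aneurysm of the great vessels, means immediate discontinuation.
- **Stopping for toxicity (12.2).** Therapy is discontinued for an event above Grade 3 when the principal investigator judges that continuing is not in the patient's interest. The investigator then decides whether "patients will resume or will be withdrawn from the study therapy".
- **Recording.** Section 8.2 follows all adverse events after any administration of study drug, and 5.3 records them over weeks 0 to 15.

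**The concern.** A Grade 4 event can be the reason a patient never completes a first cycle. If completing a cycle is the condition for entering the safety end point, membership depends partly on the outcome being measured. Two patients with the same early Grade 4 event are handled differently: the one who recovers and goes on to complete a cycle is counted, and the one who is permanently stopped is not. Under 5.3, slow recovery makes withdrawal mandatory, so the slower-resolving early events are the ones more likely to be left out.

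The timing makes this relevant. Under 5.1, radiotherapy to the first lesion begins one day after the first dose. The first exposure to the combination, whose safety is primary objective 1.1.1, therefore lies inside the window that the condition can exclude. The same patients stay in the efficacy analysis, so the two primary end points would rest on different groups.

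**Working it through.** **1. The plan's own figure.** The plan gives no number for the safety end point. Its only design calculation is for abscopal response (14.1.2 B): 28 patients, null rate 0.05, alternative 0.19, alpha 0.05, power 80%, and rejection with 3 or fewer responses. With X binomial on 28 patients:

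- P(X ≥ 4 | 0.05) = 0.0491, within 0.05.
- P(X ≥ 4 | 0.19) = 0.8065, matching the stated 80%.

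The design reproduces, and nothing in it depends on the safety set.

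**2. Which patients the condition removes.** Let k be the patients with Grade 4 toxicity among 28 treated, e those of the k permanently stopped before completing Day 14, and d the patients who stop before Day 14 without Grade 4 toxicity.

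- All-treated rate: k/28.
- Rate under 11.1.1 as written: (k − e)/(28 − e − d).

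**3. Illustration with d = 0.** The documents give neither a Grade 4 rate nor its timing, so the counts are assumed. Intervals are exact (Clopper-Pearson) 95% limits.

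| Early Grade 4 withdrawals (e) | Later Grade 4 patients (k − e) | As written | All treated |
|---|---|---|---|
| 0 | 0 | 0/28 = 0% (0–12.3) | 0/28 = 0% (0–12.3) |
| 1 | 0 | 0/27 = 0% (0–12.8) | 1/28 = 3.6% (0.1–18.3) |
| 2 | 0 | 0/26 = 0% (0–13.2) | 2/28 = 7.1% (0.9–23.5) |
| 3 | 0 | 0/25 = 0% (0–13.7) | 3/28 = 10.7% (2.3–28.2) |
| 1 | 1 | 1/27 = 3.7% (0.1–19.0) | 2/28 = 7.1% (0.9–23.5) |

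The intervals are wide and overlap. If more than 28 are treated (14.1.2 B allows enrolment of up to 56), the same counts are smaller shares: 1/56 = 1.8%.

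**4. Direction when d is not zero.** The rate as written is below the all-treated rate when 28(k − e) < k(28 − e − d), which simplifies to e/(e + d) > k/28. So it falls when Grade 4 patients are over-represented among those left out, and rises otherwise.

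- k = 3, e = 0, d = 2: 3/26 = 11.5% against 3/28 = 10.7%, a slight rise.
- k = 3, e = 1: reversal needs 1 + d > 28/3 = 9.33, so nine other early dropouts. At d = 8 the rate is 2/19 = 10.5%; at d = 9 it is 2/18 = 11.1%.

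**5. Chance that anyone is affected.** If each patient independently has probability q of permanent withdrawal for Grade 4 toxicity before completing Day 14, the chance that at least one of 28 is left out is 1 − (1 − q)^28. For assumed q of 2%, 5% and 10% this is 43%, 76% and 95%. The documents do not support any particular q.

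**The case against.** The strongest reply is that 11.1.1 is loose wording and not an exclusion rule. It does not say only, it sits in a section on anti-tumor effect, and it names no denominator. Section 14.1.1 states the safety objective without a cycle condition. Section 13 plans exact confidence limits for clinical and immune response rates and none for toxicity, so no Grade 4 estimator exists to be biased. The protocol describes the dose as well tolerated and severe radiotherapy effects as unlikely. To be left out, a patient needs an early Grade 4 event and permanent withdrawal; 5.3 and 12.2 both leave room to resume.

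Much of this stands. The reading as a restriction rests on the contrast with the wider response group in the same paragraph, not on an explicit exclusion. But whoever reports the end point must choose a group, and this is the only one the plan names for it.

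Several stronger readings are tempting and are not supported:

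- **That early events go unrecorded.** Sections 5.3 and 8.2 say otherwise.
- **That the bias can only lower the rate.** Section 5.7 lists non-toxicity reasons for stopping, such as consent withdrawal or progression, and these push it up (step 4).
- **That the cut-off is the fourteenth dose.** Section 7 gives 150 mg twice daily, so the fourteenth administration would fall on Day 7. Completion of Day 14 is the safer statement.
- **That early deaths are omitted.** Section 11.1.1 does not say how fatal events count toward an end point worded as lack of Grade 4 toxicity.
- **That a go/no-go or pausing decision is distorted.** The decision rule counts responses, and the 12.2 pause counts non-hematological toxicities of Grade 3 and above with no cycle condition.

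**Conclusion.** The point holds as a defect in the stated population for a primary end point. Section 11.1.1 conditions the safety end point on completing a 14-day cycle, a Grade 4 event can prevent completion, and no other section supplies a safety population that corrects this.

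The size cannot be derived from the documents. With 28 treated and no other early dropouts, one to three early Grade 4 withdrawals and no later event would turn 3.6% to 10.7% into 0%. With no early Grade 4 withdrawal and no other early dropouts, the two rates agree. With other early dropouts the net direction depends on who stops, although at these counts it takes many of them to offset one omitted Grade 4 patient. The consequence is confined to how the Grade 4 end point is reported; alpha, power, sample size, the response rule, the study-level pause and adverse event capture are unaffected. It should be fixed because safety of the combination is a primary objective and the correction is simple.

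**What to change.** In 11.1.1, replace the sentence on toxicity follow-up with one stating that all patients who receive any dose of LY2157299 or any fraction of protocol radiotherapy are followed for toxicity and included in the primary safety end point, whether or not a cycle is completed. Add the same group to 14.1.2 A as the safety population. A summary in patients who completed at least one cycle may be kept as supportive.

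The cost is two sentences in one amendment. No patients, visits or tests are added, since 8.2 already follows adverse events after any administration of study drug.
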